# STUDY FLOW

Patient diagnosed in the ED with hyperkalemia,  $K \geq 5.5$  mEq/l from official Laboratory test, will Start all antihyperkalemic measures, Ca gluconate need will be decided by the treating physician .  
Patient in whom K level was checked from VBG and found to be  $\geq 5.5$  mEq/l

*They will go through the same process.*

*If the official lab K level result below 5.5mEq/l, or hemolyzed patient will be excluded from the study.*

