## Selection and withdrawal of subjects:

### Inclusion and exclusion criteria

#### Inclusion criteria:

- Hyperkalemia patients with lab potassium levels equal to or more than 5.5 mEq/L ( $\geq 5.5$  mEq/L)\*.
- Adult: aged 18 years or more.
- Agreed to participate in the study.

\* If a doctor/Investigator decided to start anti-hyperkalemia medications based on the VBG/ABG patient can be enrolled but if the main laboratory value is less than 5.5 mEq/L patients will be excluded

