#### Exclusion criteria:

- Cardiac arrest
- Hyperglycemia with random blood sugar 20 mmol/L (13) or with acute diabetic complications like Diabetic Ketoacidosis / Hyperosmolar Hyperglycemic State.
- Hypoglycemia with random blood sugar (RBS)  $\leq 3.89$  mmol/l in Diabetic patients and less than 3 mmol/l in non-Diabetic patients.
- Allergies for any medication in the protocol.
- Pregnancy.
- Hemolyzed potassium level as reported by the main lab.
- Hemolysis, Tumor lysis syndrome, or Rhabdomyolysis due to the ongoing release of potassium.
- Acidosis with a pH less than 7.1 will require Sodium bicarbonate (NaHCO3).
- A patient who will need urgent Furosemide (Lasix), and or dialysis during the study period of 2 hours.
- Refused to participate.

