## **7. Study flow**

The study protocol will be for a total of 2 hours. All groups will follow the same path except the dose of insulin administered. After the result of potassium level ( $\geq 5.5$  mEq/L) patient will be screened for inclusion and exclusion criteria at the same time all other medications except insulin can be administered as the doses are fixed. Eligible patient will have to sign a

written consent if they agreed to be involved in our study. The initial data and basic labs will be collected before starting the study protocol. The incharge doctor/investigator will take the random code and write it on the data collection sheet of that patient from already prepared list/code and give the assigned nurse the medications administration card/form (see appendix: [medications administration form](#)).

Every patient will receive:

- Potassium lowering agent:
    - Intravenous Regular insulin 5 units **OR** 10 units with Glucose 50% water 50 ml over 30 minutes according to the randomization.
    - Salbutamol nebulization 10 mg in 3ml normal saline over 15 minutes.
  - The physician will decide the need of cardiac stabilizing agents (e.g Calcium Gluconate) as indicated by the physician in-charge of the patient.
- Please see [study flow chart](#) in the attachment.

5 Units insulin group	10 units insulin group
Medications to be administered: • IV Insulin Regular 5 units with Dextrose 50 % 50 ml over 30 minutes. • Salbutamol 10 mg NEB over 15 minutes.	Medications to be administered: • IV Insulin Regular 10 units with Dextrose 50 % 50 ml over 30 minutes. • Salbutamol 10 mg NEB over 15 minutes.

Figure 1: Treatment. RBS: Random Blood sugar. IV: Intravenous. NEB: Nebulization.

Initial investigations will include:

ECG, Urea and electrolytes, Creatinine, eGFR, Random blood sugar, complete blood count, Magnesium level, bone profile, phosphate level, will be attached if not sent before.

Repeated labs will be with these frequencies:

**Potassium** level: 0 and 120 minutes from medications administration time.

**Blood sugar**: 0, 60 and 120 minutes from medications administration time.

The study will be over at 2 hours (120 minutes) or by patient decision to withdraw from the study.

	0	Post involvement	
		60	120
Timeline (minutes) from medications administration	0	60	120
Eligibility screen	*		
Consent	*		
Randomization	*		
Basic labs: ECG, U&E, RBS, CBC, Mg, bone profile, PO4, VBG.	*		
Study Medication administration	* →		

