## 8. Study treatment.

### Medications for study treatment.

#### Regular insulin/ Dextrose 50%

Subjects in the emergency department with hyperkalemia will be administered regular insulin either 5 units or 10 units.

After identifying appropriate adult patients, obtaining written consent (Appendix: [Written Informed consent](#)), and labs confirmed that patient is having hyperkalemia. antihyperkalemic measures will be started, Regular insulin (5units or 10units) will be administered according to the steps below.

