## Attending physician

1. Patient will receive Salbutamol nebulization 10 mg in 3ml normal saline over 15 minutes.
2. ((The physician will decide the need of cardiac stabilizing agents (e.g Calcium Gluconate) as indicated by the physician in-charge of the patient.))
3. Will screen inclusion and exclusion criteria.
4. Explain all study procedure to the patient.
5. Obtain informed consent with signature.

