## Randomization

1. Open study envelope.
2. Take the included code in that envelope and stick it to the patient data collection sheet.
3. Give medication instructions card to the nurse in-charge of the patient

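### The Protocol's flow chart, section 7, section 8 and the inclusion footnote conflict on whether insulin may be given before randomisation, and the plan neither separately records nor analyses such dosing

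*Protocol*

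**What the plan says.** Four places in the Protocol bear on what may be given before randomisation.

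- **Section 27, study flow chart, first box.** A patient with a qualifying potassium "will Start all antihyperkalemic measures, Ca gluconate need will be decided by the treating physician". Only calcium is left to judgement; insulin is not mentioned. Patients found by venous blood gas follow the same path.
- **Section 7, Study flow.** While the patient is being screened, "all other medications except insulin can be administered as the doses are fixed".
- **Section 8, Regular insulin/Dextrose 50%.** After written consent and laboratory confirmation, "antihyperkalemic measures will be started, Regular insulin (5units or 10units) will be administered according to the steps below". Here the general term is followed directly by insulin.
- **Section 5, Inclusion criteria, footnote.** "If a doctor/Investigator decided to start anti-hyperkalemia medications based on the VBG/ABG patient can be enrolled", unless the laboratory value then proves too low. Insulin is not excepted, and the exclusion criteria do not mention insulin already given.

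The rest of the flow chart is more specific. In the attending-physician box, item 1 is "Patient will receive Salbutamol nebulization 10 mg in 3ml normal saline over 15 minutes", item 2 is optional calcium, item 3 is "Will screen inclusion and exclusion criteria" and item 5 is consent. The randomisation box comes next and includes "Give medication instructions card to the nurse in-charge of the patient". The 5 IU and 10 IU boxes follow it. The exclusion criteria include "Allergies for any medication in the protocol".

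**The concern.** The insulin dose is the only planned difference between the arms, so the plan has to be unambiguous about insulin from any other source. A clinician who follows the first box literally, or who treats on a blood gas and then enrols the patient under the footnote, could give insulin that was not randomised.

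Three features of the plan make this matter:

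- Baseline potassium is defined as the value before any medication (Protocol section 3; SAP, Secondary outcomes). The effect of early insulin would therefore count in the change score.
- In a non-inferiority trial, a smaller contrast between arms moves the result towards the conclusion the sponsor anticipates (Protocol section 25).
- The data collection sheet has one open field for other medications. It asks for no dose or time and does not separate drugs given before randomisation from those given after. No analysis in the SAP uses it.

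A second, smaller conflict lies in the attending-physician box. It lists salbutamol ahead of eligibility screening, although allergy to any protocol medication is an exclusion.

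**Working it through.** **1. The passages side by side.**

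| Place | Before consent and randomisation | Insulin |
|---|---|---|
| Flow chart, first box | All measures; calcium optional | Not excepted |
| Flow chart, later boxes | Salbutamol; calcium optional | After randomisation |
| Section 7 | Other medications, alongside screening | Excepted |
| Section 8 | Nothing; measures follow consent | After consent |
| Inclusion footnote | Treatment begun on a blood gas is allowed | Not excepted |

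On insulin, the later boxes, section 7 and section 8 agree with one another. The first box and the footnote leave the gap. On the other drugs, sections 7 and 8 differ, because section 7 allows them during screening and section 8 starts measures after consent.

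**2. When would early insulin shrink the contrast?** Suppose x extra units go to both arms (x is arithmetic only). The totals are 5 + x and 10 + x, and the difference is always 5 units. The ratio falls from 10/5 = 2.0 to 15/10 = 1.5 at x = 5, and to 20/15 = 1.33 at x = 10. Equal addition alone therefore does not remove the contrast in dose. The contrast in effect shrinks in two cases:

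- the early insulin replaces the randomised dose; or
- the dose-response is flatter at the higher totals. The Protocol's introduction gives some support for this: it cites a systematic review that found no efficacy difference between 10, 12 and 20 units. Both examples above place both arms within 10 to 20 units.

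**3. The plan's own figures.** The documents give no figure for pre-dosing. The illustration borrows 160 per arm and SD 0.62 from the sample-size sections. The dropout step reproduces (320 × 1.05 = 336). The 320 itself does not: 2 × (1.960 + 1.282)² × 0.62² / 0.2² gives 202 per arm, or 404 in total. That is a separate matter and does not affect this point.

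**4. Illustration.** Assumptions:

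- Margin M = 0.2 mmol/L. The SAP's margin of −20 units cannot be used on the potassium scale, so the sample-size effect of 0.2 is read as the margin.
- True deficit of 5 units D = 0.2 mmol/L, so any declaration of non-inferiority is false.
- f = share of patients pre-dosed; c = fraction of the contrast kept in those patients.

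Formulas:

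- SE = 0.62 × √(2/160) = 0.0693
- Observed deficit = 0.2 × (1 − f(1 − c))
- P(non-inferior) = Φ((0.2 − observed deficit)/SE − 1.96)

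Example, f = 10% and c = 0: the observed deficit is 0.18, and Φ(0.02/0.0693 − 1.96) = Φ(−1.67) = 4.7%.

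| Share pre-dosed | Contrast lost (c = 0) | Halved (c = 0.5) | Unchanged (c = 1) |
|---|---|---|---|
| 0% | 2.5% | 2.5% | 2.5% |
| 10% | 4.7% (deficit 0.18) | 3.5% (0.19) | 2.5% |
| 20% | 8.3% (0.16) | 4.7% (0.18) | 2.5% |

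**5. Would the planned analyses catch it?** The SAP requires both the intention-to-treat and per-protocol analyses to support non-inferiority, but it describes the per-protocol set in two ways. Under Populations it is the complete cases, which keeps pre-dosed patients. Under Primary outcome it is those who completed according to the protocol. That removes pre-dosed patients only if early insulin counts as a deviation, and the first box or the footnote could be cited as permitting it.

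**The case against.** The strongest reply is that the chart should be read as a whole. Its next box names only salbutamol and optional calcium before consent, the medication card is handed over at randomisation, and the dose boxes come after that. Section 6 has the nurse give medication from the envelope after consent, section 7 states the insulin exception outright, and section 24 lists incorrect drug administration or dosage as a violation. The footnote may only concern which potassium result triggers entry. The chart was also extracted from a PDF, so its arrows are not visible.

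Most of this stands. A reader might infer that the plan intends insulin before randomisation. The documents do not support that: every passage that sets out the sequence of insulin puts it after consent or randomisation. A reader might also infer that any insulin given to both arms abolishes the comparison. That does not follow either, since the 5-unit difference survives an equal addition. Large distortions can be produced by assuming large shares: about 30% false non-inferiority at 50% pre-dosed with the contrast wholly lost, about 11% with it halved. No such share appears in the documents.

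What the reply does not remove is the wording itself. The later boxes do not cancel the unqualified instruction in the first, only section 7 states the exception, and the footnote still admits treated patients without it.

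On the allergy point, section 7 runs screening alongside the other medications, so the numbered order in the chart is weak evidence that allergy would go unchecked. It is a matter for reconciliation and has no bearing on the insulin contrast.

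**Conclusion.** The point holds as an internal inconsistency that should be fixed. Taken literally, the first box conflicts with sections 7 and 8, and the inclusion footnote leaves the same gap. Insulin before randomisation is a risk created by the wording and not a step of the design.

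Its effect on the result is conditional. If early insulin replaces the study dose, or if the dose-response flattens at higher totals, the bias is towards non-inferiority; otherwise the false-positive rate is unchanged. At 10% to 20% pre-dosed, the illustration gives 4.7% to 8.3% with full loss of contrast, 3.5% to 4.7% with half, and 2.5% with none, against a nominal 2.5%. These figures rest on an assumed margin, an assumed true deficit and assumed shares. The direction is firmer than the size.

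**What to change.** 1. **Protocol.** Reconcile the inclusion footnote, sections 7 and 8, and the first two boxes of the flow chart into one statement of which treatments may precede consent and which may precede randomisation, and print it on the chart. Which rule is right is for the investigators and ethics committees; this review takes no position.
2. **Protocol.** Reconcile the order of salbutamol and eligibility screening in the attending-physician box with the allergy exclusion, again without this review choosing the rule.
3. **Data collection sheet.** Add one line for potassium-lowering drugs given before randomisation: drug, dose and time.
4. **SAP.** State that patients given non-study insulin before randomisation stay in the intention-to-treat analysis and are excluded from the per-protocol analysis. Prior insulin is settled before allocation, so this exclusion does not disturb the randomised comparison, provided it is recorded before the dose is known.

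The cost is a rewording of the affected passages, one data-sheet line and one SAP sentence. The data-sheet line should be in place early, because pre-dosing that was not recorded at the time may not be recoverable later.

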## Attending physician

1. Patient will receive Salbutamol nebulization 10 mg in 3ml normal saline over 15 minutes.
2. ((The physician will decide the need of cardiac stabilizing agents (e.g Calcium Gluconate) as indicated by the physician in-charge of the patient.))
3. Will screen inclusion and exclusion criteria.
4. Explain all study procedure to the patient.
5. Obtain informed consent with signature.

## Randomization

1. Open study envelope.
2. Take the included code in that envelope and stick it to the patient data collection sheet.
3. Give medication instructions card to the nurse in-charge of the patient

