## 1. Summary:

**Introduction:** Hyperkalemia is a serum Potassium (K) level of more than 5.5 mEq/L. It is a common emergency medicine presentation and can be life-threatening. Because of the emergency in correcting hyperkalemia, different medications are used to reduce high potassium levels to normal as soon as possible. Salbutamol inhalers, Glucose solutions, and Insulin are the main medications for managing hyperkalemia. Insulin and Dextrose shift potassium ions into body cells by stimulating the sodium/potassium ATP pump. Its effect starts in less than fifteen minutes and can last up to sixty minutes. It usually reduces potassium up to 1.1 mEq/l. There are different recommendations for Insulin dose and rate of administration for patients with hyperkalemia.

**Method:** This will be a multi-center, prospective, double-blind, non-inferiority, randomized control trial. 336 hyperkalemia patients will be randomized to the intervention group 5 units of intravenous Regular insulin and 10 units of intravenous insulin groups with fifty ml of Dextrose Fifty percent. They will be enrolled once their potassium level is 5.5mEq/L or more. The attending physician/ investigator and patient will be blinded about the dose of insulin that the patient received. Serum potassium will be measured at 0 and at 120 minutes from the start of the medications. Random blood glucose will be measured at 0, 60, and 120 minutes by Glucometer. The safety of our patients will be assessed by documentation of all adverse events, vital signs, and clinical assessment before and after drug administration. The study will end at 2 hours from insulin administration.

**Aim:** Our research idea aims to compare two recommended doses of Insulin (5 Units vs. 10 Units of Regular insulin given intravenously over thirty minutes) in the management of patients with hyperkalemia.

**Primary objective:** Mean reduction in serum potassium level using the main laboratory results at two hours from medication administration.

**Secondary objectives:** effect of initial (baseline) potassium level on the mean potassium reduction, and frequency of hypoglycemia between the 2 groups. Does the initial (baseline) blood glucose level will affect the function of insulin/dextrose in lowering potassium levels?

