## **6. Randomization**

When a patient has hyperkalemia ( $K \geq 5.5$  mEq/L) our doctor/investigator will come to explain the research to the patient/relatives and after explaining all details a written consent will be signed. Our doctor/investigator will take a random envelope from the study box to randomize the patient between 5 units or 10 units of insulin with 50 ml of 50% Dextrose and salbutamol Nebulization. The doctor will take the envelope code and place it on the data collection sheet without looking into the instructions. The Doctor will give the nurse that envelope. Each envelope will have instructions about the medications administration route and dose (see appendix: [medications administration form](#)). The Nurse will administer the medications with the documentation of starting time. Then our doctor will follow the patients and lab results for 2 hours based on the ACEP and Ministry of Health/Royal hospital protocol.

Randomization codes will be done by an online free site for having unique codes (<https://www.randomcodegenerator.com/en/generate-codes>). Eligible participants after obtaining consent will be randomly assigned to either 5 units of Intravenous insulin or 10 units of intravenous insulin. The researcher and patient will not know the dose of insulin administered.

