### Each package contains:

- **Envelope with:**
  - o Data collection sheet with unique generated number.
  - o Consent form.
  - o Instructions sheet
  - o Medication administration form (for the nurses).

Blood investigation will be sent to biochemistry lab for potassium level and other investigations, and it's the only acceptable way in the study. The study investigators will verify that study treatments are received intact and in the correct amounts.

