## Medications administration form:

### Medications administration card

(Insulin 5 units group)

- The doctor **must not know** the dose of insulin received by the patient.
- Give the patient the following medications:
  - Insulin Regular 5 units with Dextrose 50 ml of 50 % concentration intravenously (IV) over 30 minutes.
  - Salbutamol 10 mg Nebulization over 15 minutes.

Please repeat potassium level after 120 minutes from the time insulin/dextrose infusion

Repeat RBS: 60 and 120 minutes.

	60 minutes	120 minutes
Serum Potassium measurement		*
*RBS via glucometer	*	*

- If a patient become hypoglycemic (random blood sugar (RBS)  $\leq$  3.89 mmol/l in Diabetic patients and less than 3 mmol/l in non-Diabetic patients) inform the Doctor/Research assistant.
- Example: if you start insulin/Dextrose at 02:00 the infusion till 02:30 so repeat RBS at 03:00 and 04:00. Repeat U&E at 04:00.
- \*RBS: Random blood sugar. U&E: urea and electrolytes.

---

---

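### The doctor must not know the insulin dose, but the protocol conflicts on who opens the envelope and whether the doctor passes on the envelope or the dose card itself

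*Protocol*

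**What the plan says.** **The blind.** Protocol section 1 states: "The attending physician/ investigator and patient will be blinded about the dose of insulin that the patient received". Section 6 repeats this for the researcher and the patient. The medication administration card in the appendix tells the nurse that the doctor is not to learn the dose.

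**The handling.** Three places describe it.

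- Section 6: "Our doctor/investigator will take a random envelope from the study box to randomize the patient". Then: "The doctor will take the envelope code and place it on the data collection sheet without looking into the instructions". The doctor next gives the envelope to the nurse.
- Section 7: the in-charge doctor or investigator takes the code from a list prepared beforehand, writes it on the data sheet, and gives the nurse the medication card or form.
- Appendix, study flow chart, Randomization box: the envelope is opened, then "Take the included code in that envelope and stick it to the patient data collection sheet", then "Give medication instructions card to the nurse in-charge of the patient". No actor is named. The box follows the one for the attending physician, whose last step is "Obtain informed consent with signature".

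**The contents.** Section 9 lists one envelope holding the data collection sheet, the consent form, an instruction sheet and the nurses' medication form. The form in the appendix is headed "Insulin 5 units group". Section 9 also says that packages are prepared in randomization blocks and carry unique numbers.

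**The concern.** The plan relies on the doctor not knowing the dose, and that depends on how one sheet of paper is handled. Some of the written steps put that sheet in the doctor's hands, or in the same envelope as papers the doctor needs.

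A physician who knows the dose still has decisions to make within the two hours. The schedule in section 7 allows other medications as indicated. Section 5 lets the treating physician end a patient's participation. If extra potassium-lowering treatment, or withdrawal of poor responders, happened only in the 5-unit arm, the result would move towards non-inferiority. The same in the 10-unit arm would move it away.

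A laboratory potassium value prevents biased reading of the outcome. It does not prevent differential treatment before the sample, or loss of the sample. Potassium is measured only at 0 and 120 minutes, so a patient withdrawn early may have no post-baseline value unless the end-of-study assessment in section 21 is done. The SAP is not clear on whether such a patient stays in the ITT analysis: its Populations section takes all randomized subjects, while its Statistical analysis section requires at least one valid post-baseline measurement.

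**Working it through.** The plan gives no figure to reproduce on this point. The check is a comparison of the passages.

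**1. Who opens the envelope, and what is handed over?**

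| Place | Source of the code | Who opens | What the nurse receives |
|---|---|---|---|
| Section 6 | the envelope; doctor does not read the instructions | not stated | the envelope |
| Section 7 | a prepared list | not stated | the card or form, from the doctor |
| Appendix flow chart | inside the opened envelope | no actor named | the card |

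Where an actor is named (sections 6 and 7), it is the doctor or investigator who hands over. The conflict is therefore about who opens the envelope and whether the envelope or the card changes hands.

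**2. Does handling the card reveal the dose?** Yes, unless it is covered. The printed card shows the dose group in its heading and again in its first treatment line. The appendix prints the 5-unit card twice and no 10-unit card. I assume that the 10-unit card has the same layout; it must state its dose in any case for the nurse to give it. The warning that the doctor must not know is on the same sheet as the dose.

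**3. Does section 6 alone protect the blind?** Not together with section 9. Section 6 has the doctor put the code on the data collection sheet, and section 9 packs a data collection sheet in the envelope with the card. If that sheet is the one used, the envelope has to be opened to reach it. The instruction not to look is a real safeguard, but it is not a physical barrier.

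**4. Is allocation described in one way?** Section 6 gives a random draw from a box, section 7 a prepared list, and section 9 blocks. These may be stages of one process, but the text does not say how they fit. A free draw from a box does not keep block order. Section 6 names a website for generating unique codes. No block size is given, and it is not stated whether the list the doctor uses shows the arm.

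**5. Which safeguards are there?**

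- Traceability: the data sheet pairs hospital ID with study code, packages are numbered (section 9), and the nurse records the start time (section 6).
- Oversight: site visits check that randomization is followed and the blind is kept (section 22).
- Reporting: section 24 lists failure of the blind and departures from randomization as anticipated violations, and requires every violation to be documented and the principal investigator told within 24 hours.
- Not found in the public text: a requirement for sealed or opaque envelopes, use in numbered order, or a dedicated allocation log.

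The first two groups can help reconcile a swapped package after the event. None of the safeguards would stop a doctor from seeing a card, and none would show that a card had been seen.

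**6. How large could the effect be?** If a fraction f of one arm received extra lowering of g mmol/L, the difference in means would shift by f × g. The documents give neither f nor g, nor any rate of unblinding or of withdrawal by arm, so no value can be put on the shift.

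**The case against.** The best defence is that section 6 governs randomization and gives the right instruction, and that the flow chart is shorthand for it. The chart lost its boxes and arrows when the PDF was read, so the missing actor may be an artefact. The form in section 7 could be handed over inside its envelope. The word for opening the envelope also implies that it was closed. This is fair as far as it goes: the documents do not show that the blind is broken. It does not remove the conflict, because a site following section 7 or the flow chart literally would handle the card, and section 9 packs the card with the doctor's own papers.

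Several stronger readings are tempting and are not supported:

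- *There is no random allocation.* A random draw from a box of prepared packages is itself an allocation mechanism. What is missing is its reconciliation with the list and the blocks.
- *The dose is exposed before consent.* Section 6 and the flow chart both place signed consent before the envelope. Earlier exposure arises only if the consent form packed in the envelope is the one signed.
- *The envelopes are unsealed.* The text is silent on this. The gap is an unstated requirement.
- *Nothing can be traced.* Study codes, package numbers, the recorded start time and violation reporting give partial traceability.

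The room for differential treatment is also limited. Salbutamol is the same fixed dose in both arms, the non-insulin medications may be given during screening, patients needing urgent furosemide or dialysis are excluded, and the data sheet records any further antihyperkalemic measures.

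**Conclusion.** The point holds. The protocol promises that the doctor will not know the dose, but its own steps disagree on who opens the envelope and on what is passed to the nurse. Following section 7, section 9 or the flow chart as written can show the dose to the physician who decides on other medications and withdrawal. Existing controls give partial traceability; they neither prevent nor detect a viewed card.

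The size of any bias cannot be estimated, and its direction depends on the arm affected. A reader might infer a stated inflation of the false non-inferiority rate. Any such figure would rest wholly on invented rates of unblinding and co-treatment, and partly on the SAP's non-inferiority rule, which is a separate matter.

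The conclusion assumes that the 10-unit card resembles the printed 5-unit card. It is drawn from the public text, from which some pages were removed. The change should be made, because it is cheap and the blind is a stated feature of the design.

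**What to change.** Adopt one procedure and align sections 6, 7 and 9 and the appendix flow chart with it:

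1. Keep the consent form and data collection sheet outside the randomization envelope.
2. Put only the dose card in a sealed, opaque, numbered envelope, with the study code printed on the outside.
3. After signed consent, take the next number in sequence and log it against the patient.
4. Let only the administering nurse open the envelope and keep the card.
5. Have an existing team member who does not enrol patients prepare the computer-generated list and the envelopes. Keep block sizes from enrolling staff.

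The cost is repacking the envelopes, one log line per patient, one existing team member kept out of enrolment, and a protocol amendment. No patient procedure changes.
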